## 1 Summary

Title:	Multi-center Study on the Effectiveness and Safety of Artificial Intelligence Assisted System in the Clinical Application of Digestive Endoscopy Subtopic 4: Study on the effectiveness of artificial intelligence assistant system in improving the training effect of advanced physicians' enteroscopy
Short Title:	EndoAngel Study
Trial number:	EA-21-005
Research system	EndoAngel
Expected effect:	To explore whether the AI-assisted system(EndoAngel) can promote the operation training of beginners' colonoscopy.
Primary Endpoint:	1. CUSUM learning curve for colonoscopy (ACE scoring scale) 2. The difference in average test scores before and after the training
Secondary Endpoints:	1 Detection rate of advanced adenoma 2 Polyp Detection Rate, PDR 3 Average number of adenomas detected per patient 4 The detection rate of large, small and micro polyps 5 The average number of large, small and micro polyps detected 6 The detection rate of large, small and micro adenomas 7 The average number of large, small and micro adenomas detected 8 The detection rate of adenoma in different sites 9 The average number of adenomas detected in different sites Number of missed return of the sliding endoscopy/number of successful return of the sliding endoscopy 10 Real-time gut cleanliness score 11 Withdraw overspeed percentage 12 The withdraw time 13 Ratio of ileocecal reach
Trail design:	Prospective, randomized controlled, intervention, multi-center study
Participants:	Male and female subjects aged 50 years or older will require colonoscopy, and voluntarily provide imaging data of colonoscopy, and sign an informed consent form.
Sample size:	385 samples needed to be enrolled

[figure not shown]

Study Process:	
1. Subjects meeting all inclusion criteria and those failing all exclusion criteria were included in the study before colonoscopy;
 
2. Include qualified novice doctors for colonoscopy training
 
3. Patients who met the requirements were enrolled and randomly assigned as follows
 
The experimental group: received painless colonoscopy training with the assistance of the artificial intelligence assistant system, which could prompt abnormal lesions and real-time withdrawal speed, and feedback the overspeed percentage.
 
Control group: routine painless enteroscopy training, no special tips.
 
4. After colonoscopy, the teacher scored the colonoscopy using ACE scoring scale

Security	Safety incidents shall be evaluated and reported according to the quality management measures for clinical trials of medical devices

## 1.1 Time and Event Tables

Events/visits	Screening period (d -30~-1)	The day of colonoscopy(d 0)	Follow-up(d 1-14)
Informed Consent	X		
Demographic information	X		
Urine/blood pregnancy test	X		
Medical history/surgical history	X		
physical examination	X		
Selection/exclusion criteria	X		
colonoscopy		X	
Accompanying therapy	X	X	
Accompanying medication	X	X	
Adverse events		X	X
Pathological findings			X
Research completed			X

## 1.2 Flow chart

## 2 Introduction

Endoscopic diagnosis and treatment play an important role in the discovery and treatment of digestive tract diseases. Common endoscopic examination includes gastroscopy, colonoscopy, enteroscopy, capsule endoscopy, ultrasound gastroscopy, endoscopic retrograde cholangiopancreatography and other related techniques, which can be used in the diagnosis and follow-up of early gastric cancer, peptic ulcer, esophageal varices, precancerous lesions, intestinal polyps, intestinal adenomas, bowel cancer lesions, inflammatory bowel diseases, pancreatic diseases, biliary diseases, etc. At present, digestive endoscopy almost covers the diagnosis of most diseases of the digestive tract, and the digestive system diseases that can not be seen in the direct visual field of endoscope can also be realized by the related techniques based on ultrasound endoscopy, ERCP and other endoscopy (we call endoscopy here), so as to achieve the coverage of the whole digestive system. It can be seen that digestive endoscopy is of great significance for the diagnosis and development of digestive system diseases. At present, the demand for endoscopic examination in China is high, and the supply of endoscopic surgery in hospitals is short of supply, which puts forward high requirements for the proficiency and accuracy of operation doctors.

In recent years, deep learning has developed rapidly in the field of medicine. Andre Esteva et al. used deep neural networks (DNN) to classify skin cancer to an expert level. Our previous experiments show that deep learning has high accuracy in endoscopic quality monitoring, which can effectively standardize the operation of doctors, reduce the blind area of examination, and improve the quality of endoscopic examination. At the same time, it can also monitor the doctor's withdrawal time and improve the detection rate of adenoma. in the previous work of our group, we have successfully developed a deep learning-based enteroscopy speed monitoring, intestinal cleanliness evaluation, and in clinical trials to verify the effectiveness of artificial intelligence model in improving the quality of gastroscopy, enteroscopy.

Based on the above rich foundation of preliminary work and the huge demand in the field of colonoscopy training, we intend to train beginners in colonoscopy operation by comparing the cases of EndolAngel assistance and no EndolAngel assistance. To explore whether AI can promote the training of colonoscopy for beginners.

### 3 Selection

The subjects in this study were divided into endoscopists and colonoscopy patients. The endoscopists were required to be beginners without independent experience in colonoscopy, and the colonoscopy patients were male or female  $\geq 50$  years old who needed to undergo colonoscopy screening, volunteered to provide endoscopic imaging data and signed informed consent, and such patients were included in the study. 50 years of age is the recommended age for the first colonoscopy screening, so the investigation of subjects  $\geq 50$  years of age can better represent the quality of the colonoscopy test population.

#### 3.1 Endoscopic physician

➤ Inclusion criteria

Novice colonoscopists without previous experience in independent colonoscopy;

➤ Exclusion criteria

- 1) The number of operating cases does not meet the requirement of sample size
- 2) could not provide informed consent

#### 3.2 Patients

➤ Inclusion criteria

- 1) Male or female  $\geq 50$  years old;
- 2) Able to read, understand and sign informed consent
- 3) The investigator believes that the subjects can understand the process of the clinical study, are willing and able to complete all study procedures and follow-up visits, and

cooperate with the study procedures

- 4) Patients requiring colonoscopy
  - Exclusion criteria
    - 1) Have drug or alcohol abuse or mental disorder in the last 5 years
    - 2) Pregnant or lactating women
    - 3) Patients with known multiple polyp syndrome;
    - 4) patients with known inflammatory bowel disease;
    - 5) known intestinal stenosis or space-occupying tumor;
    - 6) known colon obstruction or perforation;
    - 7) patients with a history of colorectal surgery;
    - 8) Patients with previous history of allergy to pre-used spasmolysis;
    - 9) Unable to perform biopsy and polyp removal due to coagulation disorders or oral anticoagulants;
    - 10) High risk diseases or other special conditions that the investigator considers the subject unsuitable for participation in the clinical trial

### **3.3 Definition of enrollment**

After participants signed informed consent, they were randomized before colonoscopy. The randomization time was the enrollment time, and was recorded in CRF.

## **4 Endpoints**

### **4.1 Primary Endpoint**

- 1) CUSUM learning curve for colonoscopy (ACE scoring scale)
- 2) Average test score difference before and after training

### **4.2 Secondary Endpoints**

- 1) Detection rate of advanced adenoma: the numerator is the number of patients diagnosed with advanced adenomas, and the denominator is the total number of patients undergoing colonoscopy, Advanced adenoma was defined as > 10mm adenoma, villous adenoma, tubular villous adenoma, high-grade intraepithelial neoplasia, and carcinoma.

- 2) Polyp Detection Rate, PDR: the numerator is the number of patients with polyps detected by colonoscopy, and the denominator is the total number of patients who underwent colonoscopy
- 3) Average number of adenomas detected per patient: the numerator is the total number of adenomas detected by colonoscopy, and the denominator is the total number of patients undergoing colonoscopy.
- 4) The detection rate of large, small and micro polyps: the numerator is the number of patients with large ( $\geq 10$  mm), small (6-9 mm) and micro-small ( $\leq 5$  mm) polyps detected by colonoscopy, and the denominator is the total number of patients receiving colonoscopy.
- 5) The average number of large, small and micro polyps detected: the numerator is the total number of large ( $\geq 10$  mm), small (6-9 mm) and micro-small ( $\leq 5$  mm) polyps detected by colonoscopy, and denominator is the total number of patients undergoing colonoscopy.
- 6) The detection rate of large, small and micro adenomas: the numerator is the number of patients with large ( $\geq 10$  mm), small (6-9 mm) and micro-small ( $\leq 5$  mm) adenomas detected by colonoscopy, and the denominator is the total number of patients receiving colonoscopy.
- 7) The average number of large, small and micro adenomas detected: the numerator is the total number of large ( $\geq 10$  mm), small (6-9 mm) and micro-small ( $\leq 5$  mm) adenomas detected by colonoscopy, and denominator is the total number of patients undergoing colonoscopy.
- 8) The detection rate of adenoma in different sites: the numerator is the number of patients with adenomas detected in the rectum, sigmoid colon, descending colon, transverse colon, ascending colon, ileocecal region and other sites during colonoscopy, and the denominator is the total number of patients receiving colonoscopy.
- 9) The average number of adenomas detected in different sites: the numerator is the total number of adenomas detected in the rectum, sigmoid colon, descending colon, transverse colon, ascending colon, ileocecal region and other sites during colonoscopy, and the denominator is the total number of patients undergoing colonoscopy.
- 10) Number of missed return of the sliding endoscopy/number of successful return of the sliding endoscopy: the numerator is the total number of sliding endoscopy during colonoscopy, and the denominator is the number of sliding endoscopy and successful return endoscopy during colonoscopy
- 11) Real-time gut cleanliness score: during colonoscopy, a real-time intestinal cleanliness score was given by EndoAngel based on the Boston-scale Boreal Preparation Score (BBPS).

- 12) withdraw overspeed percentage:the ratio of the overspeed duration to the total duration in the process of withdrawal.
- 13) The withdraw time:the time between colonoscopy arrival at ileocecal valve and colonoscopy exit from anus.
- 14) Ratio of ileocecal reach:for a period of time, the number of colonoscopies that failed to reach the ileocecal part accounted for the proportion of the total number of colonoscopies.

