### **6.3.3 Intraoperative Managements**

- 1) Patient position: prone position with appropriate restraint.
- 2) Insertion route: according to the actual situation of the subject, usually through the anus
- 3) Patients in the control group received colonoscopy without AI assistance, and patients in the experimental group received colonoscopy with AI assistance. The advanced physician carries on the colonoscopy examination under the teacher's guidance.
- 4) After the examination, the teacher scored the colonoscopy according to the ACE scoring scale.

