### **6.3.4 Post-operative Managements**

[figure not shown]
- 1) Postoperative routine nursing
- 2) The anesthetized subjects were observed until they woke up
- 3) Patients with no lesions such as polyps were followed up until they woke up and left

the endoscopic room.

- 4) Clinical information such as the examining physician, duration of examination, sedation status, whether to ileocecal reach, bowel readiness, complications, polyp characteristics (number, location, size, color, and shape), and pathological results will be collected and recorded in a Web-based data management system.
- 5) The images and video data were collected for the functional evaluation of EndoAngel, such as the withdrawal speed, the number of sliding not returned/sliding returned, real-time intestinal preparation score, polyp detection and typing, etc.

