### **6.5 Randomization and Blinding**

#### **6.5.1 Randomization Implementation**

Randomization is conducted according to the study protocol, and the random contents are implemented in an electronic system block-randomized manner (n = 4; experimental group/control group = 1). Randomization prior to Colonoscopy to decide whether to use EndoAngel. The researchers randomized the random results generated by the electronic system, and the generated random results were stored in the research center. The random time (accurate to minute), random person, subject number and acronym were recorded in the corresponding positions of the electronic system.

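### The cleanliness score is defined as EndoAngel's live output, and the plan does not say how it, the overspeed percentage or the slide ratio are measured in control cases

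*Combined protocol and SAP*

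**What the plan says.** Three secondary endpoints in section 4.2 are involved.

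- Item 11, cleanliness, scored while the examination is under way: "a real-time intestinal cleanliness score was given by EndoAngel", based on the Boston scale. No other source is named for this endpoint.
- Item 12, overspeed percentage: "the ratio of the overspeed duration to the total duration in the process of withdrawal". Neither a measuring tool nor a speed threshold is given.
- Item 10, slide ratio: "the numerator is the total number of sliding endoscopy during colonoscopy", with a denominator that is also a count of events. No measuring tool is given.

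Section 6.3.4 item 5 connects all three to the system: "The images and video data were collected for the functional evaluation of EndoAngel, such as the withdrawal speed". It goes on to list slide counts and the real-time preparation score. The Summary (Study Process) adds that in the experimental group the system prompts on withdrawal speed and reports the overspeed percentage back to the trainee.

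On what separates the arms, section 6.5.1 says: "Randomization prior to Colonoscopy to decide whether to use EndoAngel". Section 6.3.3 says: "Patients in the control group received colonoscopy without AI assistance". The Summary describes control training as routine, with no particular prompts.

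**The concern.** An endpoint in a randomised comparison needs a value from the same instrument in both arms. Here the instrument for item 11 is also the randomised intervention, and it appears to be the main candidate for items 10 and 12. If EndoAngel is not used in a control examination, its live score is not produced there.

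Two outcomes are then possible unless the plan prevents them. Control values may be absent, leaving no arm comparison. Or they may come from another method, such as the bowel readiness entry in section 6.3.4 item 4, whose scale and rater are not stated. In that case a difference between instruments is confounded with the effect of the AI.

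Overspeed matters most, because withdrawal speed is something the intervention prompts directly. Cleanliness is less affected by the training, since it largely reflects the preparation done before the examination (section 6.3.2). It is still used in section 8.2 as a correlate of detection.

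**Working it through.** The plan gives no figure to reproduce on this point, so the check is a comparison of sections.

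**Source of each value**

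| Endpoint (4.2) | Instrument named in its definition | Link to EndoAngel elsewhere | Method stated for control cases |
|---|---|---|---|
| 10 Slide ratio | None | 6.3.4 item 5 | None |
| 11 Cleanliness | EndoAngel, live | 6.3.4 item 5 | None |
| 12 Overspeed percentage | None | Summary; 6.3.4 item 5 | None |

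**Item 11 taken literally.** The definition needs EndoAngel to score during the examination. Section 6.5.1 randomises use of EndoAngel, not display of its prompts. A case allocated to not using it therefore cannot meet the definition. Scoring a recording afterwards would not meet the wording on timing either, unless that wording is changed.

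**Items 10 and 12.** These are a ratio of counts and a ratio of durations, so in principle they can be measured without EndoAngel. The only indications of where the values come from are the Summary and section 6.3.4, and both point to EndoAngel. The gap here is an unstated method, not a definition that control cases cannot satisfy.

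**Size of the arm concerned.** With 1:1 allocation (section 6.5.1) and 385 cases (section 8.3), the control arm is 385 / 2 = 192.5, or about 192 cases.

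**Effect of mixed instruments.** Let the true arm means be μE and μC. Let EndoAngel read with systematic error bA and the control method with bB. The expected observed difference is

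(μE + bA) − (μC + bB) = (μE − μC) + (bA − bB).

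The instrument difference bA − bB enters in full and does not shrink with sample size. With the same instrument applied in the same way to both arms, bA = bB and the term vanishes. The documents give no basis for a value of bA − bB, so none is assumed.

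**Use in section 8.2.** Overspeed percentage and preparation score enter Spearman correlations with detection, slide counts enter a univariate analysis, and adenoma detection is compared by segment score with a chi-square test. Without a common measurement rule, each would rest on the experimental arm alone or on pooled values from different instruments.

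**The case against.** The strongest reply is that the plan withholds assistance from control cases, not measurement. Section 6.3.4 collects images and video without restriction by arm, and section 6.3 applies to all eligible consenting subjects. Section 3 has patients in general supplying imaging data. Section 6.3.4 also uses the real-time label for a score listed under collected images and video, so the label may name a software function and not the moment of scoring. The Summary's description of the control group would fit a system running silently. Section 7.1 refers other evaluations to a case report form that is not among the documents.

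All of this stands as evidence that same-instrument measurement is feasible. It does not show that it is planned. The stated purpose of the video is functional evaluation of EndoAngel, and no section applies the system to control cases to measure an endpoint. The wording of section 6.5.1 also sits poorly with silent running. Section 8.3 plans 3 hospitals, which could resolve the ambiguity differently.

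A further reply is that section 8.2 specifies no between-arm test for these measures. That is correct, so no specified arm test is lost. They remain secondary endpoints of a randomised trial, which implies a comparison, and the analyses that section 8.2 does specify need the same values.

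**Conclusion.** The concern holds as a gap in the measurement rule. For item 11 it is a conflict on the face of the text: a live EndoAngel score is required in examinations allocated to not using EndoAngel. For items 10 and 12 it is weaker: the control-arm method is unstated, while the only indicated source is EndoAngel. Like-for-like comparison is not assured for any of the three.

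A reader might infer that control values do not exist, or that about 192 values will be missing for each endpoint. The documents do not support that. Unrestricted video collection leaves later processing open, silent running is not excluded, and items 10 and 12 do not require EndoAngel by definition.

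The weight is moderate. These are 3 of the 14 secondary endpoints in section 4.2. The primary endpoints and the sample size do not depend on them. The change is still worth making, because overspeed is a direct indicator of what the system prompts, and control values might not be recoverable if recordings are not kept for this purpose. The conclusion assumes that no document outside those reviewed, such as the case report form, already sets the rule.

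**What to change.** In section 4.2, redefine items 10, 11 and 12 as derived for every case in both arms by the same EndoAngel version (section 9 names EA2301). Choose one of two routes and apply it at all hospitals:

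- process the recorded video from both arms after the procedure, blind to arm; or
- run the system in every case, with display and prompts hidden in control cases.

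Under the first route, remove the requirement in item 11 that the score be given live, and do not use the live displayed values for the arm comparison. Under the second, reword section 6.5.1 so that what is randomised is the assistance shown to the trainee.

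In section 6.3.4 item 5, state that the collected video is used for endpoint measurement, and give one rule for unusable or missing video that applies equally to both arms. No extension of video collection appears necessary, since the present text is not limited to one arm.

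The cost is wording in two or three sections and, under the first route, offline processing of the recordings with existing software. The downside is small: some values will be missing where video is unusable, but by the same rule in each arm.

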## 8.2 Methods

Continuous variables should be described by number of subjects, mean, standard deviation, median, minimum and maximum. The classification variables are summarized by frequency and percentage.

Spearman rank correlation analysis was used to analyze the correlation between endoscopic overspeed percentage / intestinal preparation score and adenoma detection rate / advanced adenoma detection rate / polyp detection rate.

Univariate analysis was used to analyze the correlation between the number of unreturned slides/returned slides and the detection rate of adenoma/late adenoma/polyp.

Chi-square analysis was used to analyze the detection rate of adenomas in different scores of intestinal segments.

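### Two secondary endpoints in section 4.2 are defined by formulas that contradict their names: ileocecal reach (item 14) and slide return (item 10)

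*Combined protocol and SAP*

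**What the plan says.** **Item 14.** The endpoint is called "Ratio of ileocecal reach" in the Summary (where it is item 13), in section 4.2 and in section 7.1. Only section 4.2 defines it, over an unspecified period, as "the number of colonoscopies that failed to reach the ileocecal part accounted for the proportion of the total number of colonoscopies". Section 6.3.4, item 4, records for each examination "whether to ileocecal reach".

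**Item 10.** The endpoint is called "Number of missed return of the sliding endoscopy/number of successful return of the sliding endoscopy" in the same three places. Section 4.2 then defines it in two clauses. For the top of the fraction it says "the numerator is the total number of sliding endoscopy during colonoscopy". For the bottom of the fraction it says "the denominator is the number of sliding endoscopy and successful return endoscopy during colonoscopy". Section 6.3.4, item 5, lists "the number of sliding not returned/sliding returned" among the data drawn from images and video. Section 8.2 plans a univariate analysis of "the correlation between the number of unreturned slides/returned slides and the detection rate of adenoma/late adenoma/polyp".

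Section 8.2 names no analysis specific to item 14 and no between-arm comparison for either endpoint. Apart from the univariate slide analysis, only its general descriptive summaries apply.

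**The concern.** A name and its formula should describe the same quantity. Here they do not, and nothing in the document says which one prevails. The section 4.2 text is the only operational definition an analyst has.

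For item 14, an analyst who follows the formula reports failures under a reach label. The better-trained arm then shows the lower value, and a reader who sees only the label draws the opposite conclusion about the trainees. For item 10, an analyst who follows the formula counts every slide in the numerator, including those that were returned. The result no longer measures what the name says and cannot be compared with a not-returned/returned ratio reported elsewhere.

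The stakes are the value, label and apparent direction of two of the fourteen secondary endpoints in section 4.2, and any relative comparison between arms based on them.

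**Working it through.** The documents give no expected rate for either endpoint, so there is no planned figure to reproduce. The algebra needs no assumption. All rates and counts below are assumed for illustration.

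**Item 14**

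Formula as written: failure proportion = 1 − reach proportion.

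| Reach, arm A v arm B (assumed) | Reported under the written formula | Ratio A/B, reach | Ratio A/B, as written |
|---|---|---|---|
| 95% v 85% | 5% v 15% | 95/85 = 1.12 | 5/15 = 0.33 |
| 90% v 80% | 10% v 20% | 90/80 = 1.125 | 10/20 = 0.50 |
| 70% v 60% | 30% v 40% | 70/60 = 1.17 | 30/40 = 0.75 |

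To see what happens to a test, take the 350 examinations of section 8.3, split equally (assumed) into 175 per arm.

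- Reached: 158/175 = 90.3% v 140/175 = 80.0%. The difference is +10.3 points and the ratio is 1.13.
- Failed: 17/175 = 9.7% v 35/175 = 20.0%. The difference is −10.3 points and the ratio is 0.49.
- Chi-square without continuity correction, the same for both codings: 350 × (158×35 − 140×17)² / (175 × 175 × 298 × 52) = 350 × 3150² / 474,565,000 = 7.32, p = 0.007.

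The test and the size of the absolute difference are the same. The reported value, the sign and the ratio are not.

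**Item 10**

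Let T be all slides and R those successfully returned, so T − R were not returned.

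- As named: x = (T − R)/R.
- As written, reading the denominator as slides that were successfully returned: T/R = x + 1.
- As written, reading the denominator as slides plus returns: T/(T + R) = (1 + x)/(2 + x), which always lies between 0.5 and 1.

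With T = 10 (assumed):

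| R | As named (T−R)/R | T/R | T/(T+R) |
|---|---|---|---|
| 10 | 0 | 1.00 | 0.50 |
| 8 | 0.25 | 1.25 | 0.556 |
| 6 | 0.667 | 1.667 | 0.625 |
| 5 | 1.00 | 2.00 | 0.667 |

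Comparing R = 8 with R = 6:

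| Form | Ratio | Absolute difference |
|---|---|---|
| As named | 0.25/0.667 = 0.375 | 0.42 |
| T/R | 1.25/1.667 = 0.75 | 0.42 |
| T/(T+R) | 0.556/0.625 = 0.889 | 0.07 |

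Both written forms rise with x, so ranks are kept whenever x is defined (R > 0). T/R also keeps absolute differences; T/(T + R) does not. Neither reading returns the named ratio as a formula, and both give a non-zero score to an examination with every slide returned. When R = 0, the named ratio and T/R are both undefined.

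**Can another section settle it?** For item 14, no: the Summary and section 7.1 repeat only the name, and section 6.3.4 records only the raw yes/no. For item 10, sections 6.3.4 and 8.2 mention slides not returned and slides returned, in the same order as the name, so unreturned slides are clearly the quantity of interest. They do not fix the ratio, because section 8.2 also uses slashes to list separate variables and both places may mean two counts.

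**The case against.** The strongest reply is that no information is lost and little in the planned analysis changes. Reach and failure are complements, each recoverable from the other, and the item 14 text says openly that it counts failures. A two-sided test is identical. For item 10, a constant shift of 1 leaves differences, ranks and correlations unchanged. Section 8.2 specifies no relative between-arm comparison for either endpoint, so the changed ratios above assume an effect measure as well as the input rates. For item 10, the name and the wording of sections 6.3.4 and 8.2 all point the same way, so one clause is probably a translation slip.

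Most of this stands, and it limits the severity. The changed ratios are illustrations, not planned results. The plus-1 result depends on one reading of an unclear denominator; on the other reading, differences are not preserved. A translation slip is plausible for both items.

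It does not remove the error. The current text is the plan, and it gives two incompatible instructions for each endpoint. Even the descriptive summaries that section 8.2 does specify would carry a wrong value for the label, and results tables often show the label without the definition.

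**Conclusion.** The concern holds. Item 14 is defined as the complement of its name, so value and apparent direction are reversed. Item 10 has a numerator that does not match its name; on the natural reading of its denominator the value is too high by exactly 1, and on the less natural reading it is confined to 0.5 to 1. These results follow from the definitions alone. Only the numerical examples rest on assumed rates, slide counts and an equal split of 350.

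Item 14 is the more serious because its sign flips. The error is confined to these two secondary endpoints: the primary endpoints and the sample size in section 8.3 do not depend on them. It should be corrected before analysis, but it does not threaten the main conclusions.

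**What to change.** In section 4.2:

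- **Item 14:** define it as the number of colonoscopies that reached the ileocecal region divided by all colonoscopies. Alternatively, keep the formula and rename the endpoint a failure rate in the Summary and in sections 4.2 and 7.1.
- **Item 10:** make the numerator the number of slides not returned and the denominator the number of slides successfully returned, as the name says.

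Two optional additions would help. Section 8.2 could state whether the slide ratio or the two separate counts are analysed. The sponsor could also consider slides not returned over all slides, (T − R)/T, which stays defined when no slide is returned. This is a different measure (0.20 at T = 10, R = 8), so it would need a matching name.

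The cost is two wording edits, plus a phrase in section 8.2 if that option is taken; renaming item 14 also touches the Summary and section 7.1. No new data are needed, because section 6.3.4 already collects ileocecal reach and the slides returned and not returned.
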